2.5 Overview of Formal Interim Monitoring

The study will undergo safety reviews by an ACTG-appointed Study Monitoring Committee (SMC). The first interim review will occur when 10 participants have enrolled to one select therapy group, received their first dose of vaccine after study entry, and their data through study Day 7 (7 days after the first vaccine dose) are available, or 3 months after the first participant enrolls, whichever occurs first. Subsequent reviews will occur every 6 months unless otherwise recommended by the SMC or requested by the study team.

It is not intended that the SMC will review data on immunologic outcomes. An interim review may also be convened if a safety concern is identified by the DAIDS clinical representative, the study chairs, or study statistician in consultation with the team. Enrollment will pause and the SMC will review any death that occurs on study that is deemed related to study product as determined by the site investigator. A pause in enrollment will also occur and the SMC will review if two participants experience a Grade 4 adverse event (AE) that is deemed related to study product as determined by the site investigator.

3 Outcome Measures

3.1 Primary Outcome Measures

3.1.1 Neutralizing antibody (NAb) level at least 140 days after the first dose of the study- or community-provided vaccine. (Objective 2.3.1.1)

NAb level will be measured using the pseudotyped virus reported from a single-round-of-infection neutralization assay (PSV).

3.2 Secondary Outcome Measures

- 3.2.1** Relative pre-vaccine to post-vaccine change in NAb response defined as the ratio of post-vaccine level/pre-vaccine level. The pre-vaccine NAb measurement will be obtained before the first dose of the vaccine and the post-vaccine measurement will be obtained at least 56 days after the first dose of the vaccine. (Objective 2.3.1.1)
- 3.2.2** New Grade 3 or higher AE, or SAE, or AE leading to change or discontinuation in vaccine receipt from first dose of the mRNA-based COVID-19 vaccine and through 140 days after the first dose of vaccine. (Objective 2.3.2.1)
- 3.2.3** Grade 1 or higher allergic reaction from first dose of the mRNA-based COVID-19 vaccine through the visit 56 days after the first dose of the vaccine. (Objective 2.3.2.1)
- 3.2.4** Grade 2 or higher injection site reaction from first dose of the mRNA-based COVID-19 vaccine through the visit 56 days after the first dose of the vaccine. (Objective 2.3.2.1)
- 3.2.5** Relative pre-vaccine to post-vaccine change in NAb response defined as the ratio of post-vaccine level/pre-vaccine level by received vaccine, i.e., Moderna versus Pfizer. The pre-vaccine NAb measurement will be obtained before the first dose of the vaccine, and the post-vaccine measurement will be obtained at least 56 days after the first dose of the vaccine. (Objective 2.3.1.1)

4 General Considerations

The aim of this study is to describe immunologic responses to mRNA-based SARS-CoV-2 vaccine among individuals who previously received investigational therapy in ACTIV-2/A5401 for SARS-CoV-2 infection in comparison to individuals who received a placebo. As ACTIV-2/A5401 is expected to change from using a placebo control to an active control, this study's aim will also evolve to describe immunologic responses to mRNA-based SARS-CoV-2 vaccine among individuals who previously received investigational therapy in ACTIV-2/A5401 for SARS-CoV-2 infection in comparison to individuals who received an active control.

Estimates and confidence intervals for NAb will be obtained by using a log base 10 transformation on the PSV values, then using linear regression with an indicator variable for prior select COVID-19 therapy exposure versus placebo using standard methods, assuming that the \log_{10} NAb responses are approximately normally distributed within exposure group.

4.1 Analysis Sets and subgroups

4.1.1 ACTIV-2/A5401 active therapy/placebo Response Set

All enrolled participants who were previously enrolled to active therapy or placebo in ACTIV-2/A5401 who received at least one dose of vaccine.

4.1.2 Safety Set

All enrolled participants who received the first dose of vaccine

Subgroups or subpopulations of interest

- 4.1.3** Subgroups defined by levels of sex, if sample size permits
- 4.1.4** Subgroups defined by levels of race/ethnicity, if sample size permits

5 Estimands

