Participants will receive their first Moderna mRNA-1273 COVID-19 vaccine dose in the community. Their second Moderna mRNA-1273 dose will be provided by the study (100 µg [0.5 mL] to be administered IM 28 days after their first dose).

NOTE: These participants may enter the study before or after their first vaccine dose.

Participants without prior history of SARS-CoV-2 infection

Participants will receive the following study-provided regimen: Moderna mRNA-1273 COVID-19 vaccine, 100 µg (0.5 mL) to be administered IM at Entry and Day 28.

c. Section 3.0 Study Design

The last sentence of the second paragraph: “Participants will have blood collected and immune responses measured before the first vaccine dose (if feasible), and before the second dose of vaccine (e.g., 28 days later for Moderna vaccine and 21 days later for Pfizer vaccine if given in the community) (**if feasible**), and 56 (**if feasible**), 140, 365, and 730 days after **their first vaccine dose** (Figure 3.0-1).”

d. Section 4.2 Exclusion Criterion 4.2.2

This criterion was revised as follows: “For participants who are in, or who have completed, the ACTIV-2/A5401 trial: Self-report of receipt of the ~~second~~ **first** dose of an mRNA-based COVID-19 vaccine **140 days or more before A5404 enrollment.**”

e. Section 5.1.1 Regimen and Duration

Participants will receive the following study-provided regimen: Moderna mRNA-1273 COVID-19 vaccine, 100 µg (0.5 mL) to be administered intramuscularly (IM) at **Entry** and Day 28.

Or

Participants will receive a two-dose series of a community-provided mRNA-based COVID-19 vaccine that has received FDA EUA or FDA approval.

NOTE: Participants who receive a community-provided mRNA-based COVID-19 vaccine may receive their **first and second** COVID-19 vaccine dose(s) before study entry.

Or

Participants will receive (or have recently received) a community-provided Moderna mRNA-1273 COVID-19 vaccine at (or before) **Entry** and study-provided Moderna mRNA-1273 COVID-19 vaccine, 100 µg (0.5 mL) to be administered intramuscularly (IM) at at least 28 days apart.

f. Section 6.1, Table 6.1-3

The title of this section was changed to, “~~Community Provided mRNA-based COVID-19 Vaccine~~ Schedule of Evaluations for ACTIV-2/A5401 Participants **who Received First Dose of a Community-Provided mRNA-based COVID-19 Vaccine Before Entry or Will Receive First Dose After Entry**”

g. Section 6.1, Table 6.1-4 was added:

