56 and 140 Days Post-Vaccination #1 for ACTIV-2/A5401 Participants Who Received First and Second Doses of a Community-Provided mRNA-based COVID-19 Vaccine before Entry

- **56 days post-vaccination #1 timepoint:**
 - This visit will not be conducted if the participant enrolls more than 56 days after their first vaccine dose.
 - This visit may be combined with the Entry visit if the participant enrolls between 56 and 63 days after their first mRNA COVID-19 vaccine dose. Evaluations indicated at both timepoints will be conducted only once.
- **140 days post-vaccination #1 timepoint:** This visit may be combined with the Entry visit if the participant enrolls between 133 and 147 days after their first mRNA COVID-19 vaccine dose. Evaluations indicated at both timepoints will be conducted only once.

k. Section 6.3.7 Vaccine Administration

The first sub-section title was changed to, “Documentation of Community-Provided COVID-19 Vaccination”

l. Section 6.3.8 Vaccine Symptom Screen

The first sentence has been revised to, “For participants who receive community-provided mRNA-based COVID-19 vaccine: If the participant enrolls >14 days after the first or second dose of their vaccine, then a Vaccine Symptom Screen is not collected for the doses provided prior to enrollment.”

4. Section 4.1, Inclusion Criterion 4.1.3:

The following note was added.

NOTES:

- Selected investigational therapies will be posted on the A5404 PSWP.
- **For participants who received camostat or the active comparator/placebo for camostat: Receipt of ≥50% of the doses indicated in ACTIV-2/A5401.**

5. Section 5.2, Study Product Formulation and Preparation**a. In section 5.2.1 Formulation and Storage, the following modifications have been made:**

The Moderna mRNA-1273 COVID-19 vaccine is supplied as a frozen suspension, stored between ~~-25-50°~~ to -15°C, in multi-dose vials, and does not contain a preservative. ~~Store in the original carton to p~~ **Protect** from light. Do not store on dry ice or below ~~-40-50°C~~. The Moderna mRNA-1273 COVID-19 vaccine is white to off-white suspension. It may contain white or translucent product-related particulates.

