2.1 Study Design

A5404 is a phase IV, open-label, sub-study of ACTIV-2/A5401 aiming to evaluate how prior investigational therapy for COVID-19 versus comparator (placebo or active comparator) affects vaccine response. This is a non-randomized study designed to have reasonable precision to estimate the difference in immune response between those with versus without prior select investigational therapy for COVID-19. Results will be interpreted in the context of available information from outside the study when analyses are completed.

The study will enroll a target of 70 participants from each ACTIV-2/A5401 select therapy group (comprised of individuals exposed to active treatment and individuals exposed to the corresponding placebo or active comparator). In addition, up to 70 individuals without prior history of SARS-CoV-2 infection will be enrolled based on vaccine supply at each A5404 site. The total sample size will depend on how many therapies are selected from ACTIV-2/A5401. The ratio of participants with active therapy exposure versus corresponding comparator exposure in ACTIV-2/A5401 is also unknown a priori, as the randomization ratio for ACTIV-2/A5401 study depends on the number of agents concurrently enrolling. If the target sample of 70 participants for a select therapy group is not able to be met from Phase II participants in the ACTIV-2/A5401 trial, then enrollment will open to participants from the respective Phase III group in ACTIV-2/A5401.

Eligible participants will receive mRNA COVID-19 vaccine in one of three ways:

Cohort 1: ACTIV-2/A5401 participants

Participants will receive one of the following regimens:

Cohort 1a: Moderna mRNA-1273 COVID-19 vaccine, 100 µg (0.5 mL) to be administered intramuscularly (IM) at Entry and Day 28. Both doses will be provided by the study.

Or

Cohort 1b: Participants will receive a two-dose series of a community-provided mRNA-based COVID-19 vaccine that has received FDA EUA or FDA approval (e.g., Moderna or Pfizer). Vaccine will not be provided by the study.

NOTE: These participants may enter the study before their first vaccine dose, after their first vaccine dose, or after their second vaccine dose.

Or

Cohort 1c: Participants will receive their first Moderna mRNA-1273 COVID-19 vaccine dose in the community. Their second Moderna mRNA-1273 dose will be provided by the study (100 µg [0.5 mL] to be administered IM 28 days after their first dose).

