5.3 Secondary Safety Estimand

Secondary Objective 2.3.2.1: To explore the safety of mRNA-based COVID-19 vaccines among participants with prior COVID-19 who received investigational therapy or its comparator for COVID-19 and persons who are SARS-CoV-2 naïve.
	
Estimand description	Occurrence of adverse events up to 56 and 140 days after receiving the first dose of an mRNA-based COVID-19 vaccine among individuals receiving at least one dose of the vaccine with and without prior history of COVID-19.
Treatment	
Cohort 1a: Moderna mRNA-1273 COVID-19 vaccine, 100 µg (0.5 mL) to be administered intramuscularly (IM) at Entry and Day 28. Both doses will be provided by the study.
 
Or
 
Cohort 1b: Participants will receive a two-dose series of a community-provided mRNA-based COVID-19 vaccine that has received FDA EUA or FDA approval (e.g., Moderna or Pfizer). Vaccine will not be provided by the study.
 
NOTE: These participants may enter the study before their first vaccine dose, after their first vaccine dose, or after their second vaccine dose.
 
Or
 
Cohort 1c: Participants will receive their first Moderna mRNA-1273 COVID-19 vaccine dose in the community. Their second Moderna mRNA-1273 dose will be provided by the study (100 µg [0.5 mL] to be administered IM 28 days after their first dose).
 
Or
 
Cohort 2: Participants will receive the following study-provided regimen: Moderna mRNA-1273 COVID-19 vaccine, 100 µg (0.5 mL) to be administered IM at Entry and Day 28.

Target population	Analysis sets
Individuals who received an mRNA-based COVID-19 vaccine with and without a prior history of COVID-19.	Safety Set (all enrolled participants who received at least one dose of vaccine)
Variable	Outcome measures
Occurrence of an adverse event up to 56 and 140 days after first dose of an mRNA-based COVID-19 vaccine.	
New Grade 3 or higher AE, SAE, or AE leading to change or discontinuation in vaccine receipt from first dose of the mRNA-based COVID-19 vaccine and through 140 days after the first dose of the vaccine.
 
Grade 1 or higher allergic reaction from first dose of the mRNA-based COVID-19 vaccine through the visit 56 days after the first dose of the vaccine.
 
Grade 2 or higher injection site reaction from first dose of the mRNA-based COVID-19 vaccine through the visit 56 days after the first dose of the vaccine.

Handling of intercurrent events	Handling of missing data

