
The following intercurrent events are relevant to the estimand:
 
 1. Reinfection with SARS-CoV-2 between first and second vaccine doses. Post vaccination observations through the respective time point of interest (56 or 140 days) after first vaccine dose will be used to determine the variable (treatment policy strategy) 2. Discontinuation of treatment after first vaccine dose due to safety event(s). All observations through the respective time point of interest (56 or 140 days) after first vaccine dose will be used to determine the variable (treatment policy strategy) 3. Discontinuation of treatment after first dose of vaccine due to non-safety reasons. All observations through the respective time point of interest (56 or 140 days) after first vaccine dose will be used to determine the variable (treatment policy strategy) 4. Death prohibiting subsequent existence of the variable. Observations before death will be used to determine the variable (while alive strategy) 	
Participants who discontinue follow-up before the respective time point of interest (56 or 140 days) after the first dose of the vaccine will have their outcome measures determined based on data available until the time of study discontinuation. This implicitly assumes that the participants would not have had an applicable AE had they been observed to the time point of interest.
 
Sensitivity analyses:
 
We will consider those participants who discontinued follow-up before the time point of interest (56 or 140 days) after the first vaccine dose as having at least one adverse event.
 
We will only include participants who were not re-infected with SARS-CoV-2 between first and second doses of the vaccine.

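### SAP 5.3 counts reactions from first dose over all dosed enrollees but has no rule for doses given more than 14 days before entry, which get no symptom screen

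*SAP*

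**What the plan says.** **Outcome and denominator.** SAP 3.2.3 defines "Grade 1 or higher allergic reaction from first dose of the mRNA-based COVID-19 vaccine through the visit 56 days after the first dose" of vaccine; 3.2.4 uses the same window for Grade 2 or higher injection-site reactions. SAP 4.1.2 takes as the Safety Set "All enrolled participants who received the first dose of vaccine", and the analysis-set row of 5.3 repeats this as anyone with at least one dose. Neither sets a condition on when the dose was given relative to entry. For each outcome 5.3 plans a proportion with an exact 95% interval in three groups: active therapy (including Camostat), placebo, and participants without prior COVID-19.

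**Entry after dosing.** The treatment row of 5.3 says of Cohort 1b: "These participants may enter the study before their first vaccine dose, after their first vaccine dose, or after their second vaccine dose". Cohort 1c may enter after its first dose, but "Their second Moderna mRNA-1273 dose will be provided by the study" (SAP 2.1). LOA #1 (Exclusion Criterion 4.2.2) excludes ACTIV-2 participants only if the first dose was "140 days or more before A5404 enrollment", so entry is possible up to Day 139.

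**Collection of reactions.** LOA #1, Section 6.3.8: "If the participant enrolls >14 days after the first or second dose of their vaccine, then a Vaccine Symptom Screen is not collected" for doses given before enrollment.

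**Missing data.** The rule in 5.3 concerns "Participants who discontinue follow-up before the respective time point of interest (56 or 140 days) after the first dose of the vaccine". Its worst-case sensitivity analysis covers the same people; the other sensitivity analysis is about reinfection. SAP 5.2, by contrast, names participants vaccinated before entry and excludes them from the antibody-change analysis.

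**Reporting.** SAP 7.6 describes its reaction summaries as both post-entry and starting from the first dose. SAP 7.5 plans counts of participants vaccinated before entry and the days from first vaccine to entry.

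**The concern.** A proportion is interpretable only if everyone in the denominator could have contributed an event to the numerator. Here the window opens at the first dose, but for some participants the main instrument for reactions may not have been applied to one or both doses. If those people stay in the denominator and their reactions come from nowhere else, they count as reaction-free without having been observed. The proportion is then too low, and the exact interval is too narrow for the information available.

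Cohort 2 receives both doses on study and is followed from the first, so the naïve group has no such loss. A reader setting the three groups of 5.3 side by side would be comparing different degrees of ascertainment. The active-versus-placebo picture is distorted only if the share dosed well before entry differs between those two groups.

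The post-entry wording in 7.6 adds a second problem. If it governs the numerator, someone who enters after the Day 56 window has no countable reaction, even if the medical history recorded one. Someone who enters on Day 10 and reports a Day 1 reaction on the screen would also have it discarded.

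**Working it through.** **The plan's own figures.** No rate, sample size or precision is stated for the safety estimand, so there is nothing to reproduce on this point. The precision intervals in SAP 2.4 and its continuation concern antibody ratios. They reproduce with a t quantile on 68 df, but do not bear on this question.

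**Step 1: who can lack a screen.** This reads LOA 6.3.8 dose by dose, the more lenient reading.

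| Cohort | Entry relative to doses | Screen that can be missing |
|---|---|---|
| 1a, 2 | dose 1 at Entry | none |
| 1b | before dose 1 up to Day 139 after it | neither, dose 1 only, or both |
| 1c | before or after dose 1; dose 2 from the study | neither, or dose 1 only |

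Entry by Day 14 after dose 1 loses no screen. The 5.3 groups are built on ACTIV-2 treatment, so any affected 1b or 1c participants fall in the active or placebo group.

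**Step 2: expected size of the bias.** Inputs, all assumed because the documents give none: true participant-level proportion p = 0.20; two doses with equal, independent risk q; share f of a group unscreened; share r of unscreened reactions captured elsewhere.

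- q = 1 − √(1 − 0.20) = 0.1056.
- Dose 1 unscreened: p_B = 1 − (1 − rq)(1 − q).
- Both unscreened: p_C = 1 − (1 − rq)².
- Expected estimate = (1 − f)p + f·p_B, or (1 − f)p + f·p_C.

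Example, f = 0.25, both unscreened, r = 0.5: p_C = 1 − (0.9472)² = 0.1028, so 0.75 × 0.20 + 0.25 × 0.1028 = 0.176.

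| Unscreened | f | r = 0 | r = 0.5 | r = 1 |
|---|---|---|---|---|
| dose 1 only | 0.25 | 17.6% | 18.8% | 20.0% |
| dose 1 only | 0.50 | 15.3% | 17.6% | 20.0% |
| both | 0.25 | 15.0% | 17.6% | 20.0% |
| both | 0.50 | 10.0% | 15.1% | 20.0% |

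With f = 0 or r = 1 there is no bias, provided the captured reactions are also counted.

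**Step 3: effect on the exact interval.** SAP 2.4 gives 43 enrolled in total. Assume 14 per group (43/3 ≈ 14.3), two events seen, r = 0, and k people unscreened for both doses. Intervals are Clopper-Pearson 95%.

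| k | As planned, 2/14 | Among those observed, 2/(14 − k) | Worst case, (2 + k)/14 |
|---|---|---|---|
| 0 | 14.3% (1.8–42.8) | 14.3% (1.8–42.8) | 14.3% (1.8–42.8) |
| 1 | 14.3% (1.8–42.8) | 15.4% (1.9–45.4) | 21.4% (4.7–50.8) |
| 4 | 14.3% (1.8–42.8) | 20.0% (2.5–55.6) | 42.9% (17.7–71.1) |
| 7 | 14.3% (1.8–42.8) | 28.6% (3.7–71.0) | 64.3% (35.1–87.2) |

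The planned result is the same whatever k is. One affected person hardly matters; four of 14 does.

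**Step 4: the Day 140 outcome.** SAP 3.2.2 and the outcome row of 5.3 define a composite: a new Grade 3 or higher AE, an SAE, or an AE that changes or stops vaccine receipt. SAP 7.6 summarises that composite. The summary-measure and analysis rows of 5.3, and 7.9, name Grade 3 or higher AEs only. No proportion with an exact interval is therefore planned for the outcome as defined.

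**The case against.** The strongest reply is that nobody may be affected. SAP 1.2 records that version 3.0, finalised in January 2023 after accrual closed in February 2022, dropped the Retrospective Safety Set as no longer relevant. The previous version had adapted that set for people with both doses before entry. The Cohort 1b note may simply repeat design text, and a planned table in 7.5 does not show that anyone entered late. This stands as a limit: the count may be zero. It does not close the point, because the documents give no count and state no replacement rule.

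Second, the screen may not be the only source. Table 6.1-4 schedules medical history and clinical assessments at screening and entry, 7.6 lists every AE by participant, and the base text on AE reporting is not available here. This also stands, and is why the bias is stated conditionally. It does not help where the post-entry wording in 7.6 would discard a captured reaction.

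Third, 7.5 already discloses most of the relevant timing; only dose-2 timing or screen status is missing. Fourth, the objective is exploratory and descriptive, with no between-group contrast in 5.3, and the intervals are wide in any case. Both are fair and keep the severity down.

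A reader might go further and infer that the reported reaction rates are biased, or that 5.3 scores an unscreened dose as no event. The documents support neither. Scoring as no event is an inference from the denominator, by analogy with the discontinuation rule; the Analysis Implementation Plan, which holds the coding descriptions, is not available. Nor has the 3.2.2 composite been abandoned, since the outcome row of 5.3 and 7.6 both carry it.

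**Conclusion.** The gap holds in conditional form. As written, the numerator and denominator in 5.3 need not match for anyone in Cohort 1b or 1c dosed more than 14 days before entry, and 7.6 and 5.3 give different starting points for counting. If such doses exist and their reactions are neither captured nor counted from another source, the active and placebo proportions are biased downward and their exact intervals treat unobserved doses as observed. The naïve group is unaffected.

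The size is unknown and may be zero. All magnitudes above rest on an assumed 20% risk, equal and independent doses, assumed unscreened shares and equal groups of 14. This is a minor to moderate point: it could yield a misleading descriptive estimate, not a wrong test. The composite mismatch in 5.3 and 7.9 is a separate error, plain from the text, and does not depend on these assumptions.

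**What to change.** 1. In SAP 7.6, reconcile post-entry with from first dose, and state which governs the proportions in 5.3 and 7.9.
2. Add dose-2 timing or screen status to the 7.5 tables, by 5.3 group: screened for both doses, one dose, or neither.
3. If no dose was given more than 14 days before entry, say so and stop there.
4. Otherwise keep the planned 3.2.3 and 3.2.4 proportions and add a supplementary analysis by dose. Limit it to participants observed for that dose (enrolled before it, or screened within 14 days after it), and show the number assessed. Extend the existing worst-case analysis in 5.3 to unscreened doses, presented as a bound.
5. Separately, give the proportion and exact 95% interval for the full 3.2.2 composite in the summary-measure and analysis rows of 5.3 and in 7.9.

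**Cost.** No new data collection should be needed: 7.5 already requires first-dose and entry dates, and community vaccination is documented at entry. Denominators shrink and intervals widen. Restricting to observed doses shifts the mix toward study-provided Moderna, so it exchanges some under-ascertainment for some selection. The bound may be too wide to inform. SAP 1.2 says the final report was conducted under version 3.0, so the additions would carry a post hoc label.
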